**Table 7-5a Local ECG collection plan**

Cycle	Patients	Day	Time	ECG Type
Screening	All	-7 to -1	Anytime	Triplicate 12 Lead
1	All	Day 15 	Pre-dose 	Triplicate 12 Lead

Cycle	Patients	Day	Time	ECG Type
	All		2h post-dose ( $\pm$ 15 min)	Triplicate 12 Lead
	All		4 h post-dose ( $\pm$ 15 min)	Triplicate 12 Lead
2	All	Day 1 	Pre-dose 	Triplicate 12 Lead
	All	Day 15 	Pre-dose 	Triplicate 12 Lead
			2h post-dose ( $\pm$ 15 min)	Triplicate 12 Lead
3	All	Day 1	Pre-dose 	Triplicate 12 Lead
			2h post-dose ( $\pm$ 15 min)	Triplicate 12 Lead
4	All	Day 1	Pre-dose 	Triplicate 12 Lead
5	All	Day 1	Pre-dose 	Triplicate 12 Lead
6	All	Day 1	Pre-dose 	Triplicate 12 Lead
			2h post-dose ( $\pm$ 15 min)	Triplicate 12 Lead
All other cycles	All	As clinically indicated	Anytime	Triplicate 12 Lead
EOT			Anytime	Triplicate 12 Lead
Unscheduled ECG			Anytime	Triplicate 12 Lead
 The exact date and time of dosing must be recorded on the appropriate eCRF				

**Table 7-5b Local ECG collection plan – for crossover patients**

Patients	Cross Over Cycle	Day / time	ECG type
All	1	Day 1 / Pre-dose 	Triplicate 12 Lead
All	1	Day 15 / anytime	Triplicate 12 Lead
All	2	Day 1 / anytime	Triplicate 12 Lead
All	2	Day 15 / anytime	Triplicate 12 Lead
All	All other cycles	As clinically indicated	Triplicate 12 Lead
All	EOT	Anytime	Triplicate 12 Lead
All	Unscheduled ECG	Anytime	Triplicate 12 Lead
 The exact date and time of dosing must be recorded on the appropriate eCRF			

[figure not shown]
Patients in the placebo arm who elect to transition from placebo to LEE011 must have ECG for QT assessment on the first day **before** the administration of LEE011. **LEE011 should be initiated only in patients with QTcF values <450 msec.** ECGs should be repeated on cross-over Cycle 1 Day 15, Cycle 2 Day 1, Day 15 and then as clinically indicated as per [Table 7-5b](#).

In order for an accurate evaluation of baseline QTcF, a total of three 12-lead ECGs will be performed within 7 days prior to randomization (at screening between Day -7 and Day -1).

**Note:** In order to ensure ECG evaluation is received from the central laboratory for eligibility assessment, it is advisable to perform the ECG at least 24 hours prior the scheduled randomization date.

If a QTcF value of  $\geq$  481 ms is observed in a single ECG or as the average (when collected as a triplicate) at any time after randomization, study treatment must be interrupted, repeat ECG(s) and follow management guidelines detailed in [Table 6-6](#).

An unscheduled ECG may be repeated at the discretion of the investigator at any time during the study and as clinically indicated. Unscheduled ECGs with clinically significant findings

should be collected in triplicate. Additionally, a local cardiologist may be consulted at any time during the study at the discretion of the investigator. If an unscheduled ECG is performed at an external medical facility, a copy of the ECG should be obtained and forwarded to the ECG central laboratory, and a copy kept in the source documents at the study site. Centrally reviewed ECG findings should be documented on the ECG CRF page.

In the event that a QTcF value of  $\geq 501$ ms is observed or if an unscheduled ECG is performed for safety reasons, it is recommended to collect a time-matched PK sample and record the time and date of the last study drug intake to determine the drug exposure. If PK sampling is possible, refer to the section PK sampling and detail appropriate procedures to be followed ([Section 7.2.3](#)).

All ECGs including unscheduled triplicate ECGs with clinically relevant findings, collected during the study should be transmitted to the central laboratory and will be centrally reviewed by an independent reviewer. The results of the centrally assessed ECGs are electronically transferred into the clinical database.

Any original ECG not transmitted to a central laboratory should be forwarded for central review. Interpretation of the tracing must be made by a qualified physician and documented on the ECG CRF page. Each ECG tracing should be labeled with the study number, patient initials (where regulations permit), patient number, date, and kept in the source documents at the study site. Clinically significant ECG abnormalities present at screening when the patient signed informed consent should be reported on the Medical History CRF page. New or worsened clinically significant findings occurring after informed consent must be recorded on the Adverse Events CRF page.

#### 7.2.2.6.2 Cardiac imaging - MUGA (multiple gated acquisition) scan or echocardiogram

Cardiac imaging will be performed by MUGA scan or ECHO in order to assess the left ventricular ejection fraction. This assessment will be performed according to the schedule given in [Table 7-1a](#) and [Table 7-1b](#).

The same technique (MUGA or ECHO) must be used during the course of the trial, and the method used will be recorded in the eCRF. Only clinically significant abnormalities should be reported in the Adverse Events eCRF.

[figure not shown]
In case a patient develops left ventricular systolic dysfunction while on study treatment dose adjustment guidelines described in [Table 6-7](#) must be followed.

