### **Changes to the protocol:**

Changes to specific sections of the protocol are shown in the track changes version of the protocol using strike through font for deletions and underlined for insertions.

The changes made to the protocol due to this amendment are incorporated in the following sections:

- Summary section of the protocol has been updated to maintain consistency within the main body of the protocol.
- Section 4.3 End of Study and 6.1 Definition of Study and Study Treatment sections were updated to note that the study will be unblinded and patients will have the opportunity to transition from placebo to investigational treatment (LEE011).
- Figure 4-1 Study Design has been updated to reflect the transition from placebo to investigational treatment (LEE011).
- Section 6.3.2 Treatment assignment and randomization was updated to clarify that the study will be unblinded and patients will have the opportunity to cross-over from placebo to LEE011.
- Section 6.3.3 Treatment unblinding was updated to clarify that the study will be unblinded.
- Section 6.5.1.2.3 Added Toxic Epidermal Necrolysis (TEN) to the guidance for all other Adverse Reactions.
- Section 6.5.1.2.4 Adjustment of starting dose in patients with hepatic impairment and renal impairment has been updated based on new information from pharmacokinetic analysis.
- Table 6-5 Dose adjustment recommendations for hepatic toxicities was updated as per latest Program Standard Language.
- Table 6.6 Additional follow-up for QTcF prolongation: wording related to PK assessment was removed.
- Table 6-7 added to include dose adjustment and management recommendations on Interstitial Lung Disease (ILD)/pneumonitis.
- Section 7-1 Study Flow and Assessments were updated for all patients and additional clarification and instruction was given for cross-over patients.
  - Table 7-1a was updated to clarify study assessments.
  - Table 7-1b was added to clarify assessments for cross-over patients.

- Section 7.2.1.3 has been updated to clarify that radiology review from the blinded independent review committee has been completed.
- Section 7.2.2.5.6 Hepatic Safety Markers: was updated to clarify hepatic safety markers will no longer be collected.
- Section 7.2.2.6.1 Cardiac Assessments was updated to clarify that all ECGs will be performed locally and the schedule of assessments was updated for all patients.

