**Table 6-7 Ribociclib/placebo dose adjustment and management recommendation for ILD/pneumonitis (CTCAE v4.03)**

Grade	Dose Adjustment and Management Recommendations
1 (asymptomatic)	No dose adjustment required. Initiate appropriate medical therapy and monitor as clinically indicated.
2 (symptomatic)	Interrupt ribociclib dose until recovery to Grade $\leq 1$ , then resume ribociclib at the next lower dose level*.
3 and 4 (severe)	Discontinue ribociclib

\*An individualized benefit-risk assessment should be performed before resuming ribociclib

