### 6.5.1.2.3 Guidance for all other adverse reactions

Consider performing an analysis of serum potassium, calcium, phosphorus, and magnesium for all adverse reactions, if indicated. If electrolyte values are outside of the normal range, , interrupt ribociclib/placebo administration, correct electrolytes with supplements or appropriate

therapy as soon as possible, and repeat electrolyte testing until documented normalization of the electrolytes.

Patients who experience non-acute renal impairment of grade 2 or higher during the treatment period should discontinue ribociclib/ placebo treatment and should be followed for safety assessments. For all other adverse events, including Toxic Epidermal Necrolysis (TEN), which is a grade 4 event by CTCAE, please follow recommendations in [Table 6-8](#).

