**Table 6-8 Ribociclib/placebo dose adjustment and management recommendation for all other adverse reactions**

Grade	Dose Adjustment and Management Recommendations
1	No dose adjustment recommended. Initiate appropriate medical therapy and monitor.
2	Dose interruption until recovery to grade $\leq 1$ . Initiate appropriate medical therapy and monitor. Re-initiate ribociclib/placebo at the same dose. If the same toxicity recurs at grade 2, interrupt ribociclib/placebo until recovery to grade $\leq 1$ . Re-initiate ribociclib/placebo at the next lower dose level.
3	Dose interruption until recovery to grade $\leq 1$ . Initiate appropriate medical therapy and monitor. Re-initiate ribociclib/placebo at the next lower dose level. If toxicity recurs at grade 2: temporary dose interruption until recovery to grade $\leq 1$ and reduce ribociclib/placebo dose the next lower dose level. If toxicity recurs at grade 3, discontinue ribociclib/placebo.
4	Discontinue ribociclib/placebo and treat with appropriate medical therapy.

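### Protocol Section 7.2.2.6.2 sends left ventricular systolic dysfunction to Table 6-7, the ILD/pneumonitis table, instead of Table 6-8

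*Protocol*

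**What the plan says.** Protocol Section 7.2.2.6.2 (cardiac imaging) contains an operative dosing instruction: "In case a patient develops left ventricular systolic dysfunction while on study treatment dose adjustment guidelines described in" Table 6-7, with following them stated as an obligation.

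Table 6-7 is titled "Ribociclib/placebo dose adjustment and management recommendation for ILD/pneumonitis (CTCAE v4.03"). For grade 2 it interrupts ribociclib until recovery, "then resume ribociclib at the next lower dose level", with the footnote "An individualized benefit-risk assessment should be performed before resuming ribociclib". For grades 3 and 4 it discontinues ribociclib.

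Section 6.5.1.2.3 gives the general rule: "For all other adverse events, including Toxic Epidermal Necrolysis (TEN), which is a grade 4 event by CTCAE, please follow recommendations in" Table 6-8. In Table 6-8, the grade 2 row interrupts until recovery and continues: "Initiate appropriate medical therapy and monitor. Re-initiate ribociclib/placebo at the same dose. If the same toxicity recurs at grade 2", at which point the dose goes down one level. The grade 3 row interrupts and restarts one level lower; on recurrence, "If toxicity recurs at grade 3, discontinue ribociclib/placebo".

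Section 6.5.1.2 (text under Table 6-3) lets the treating physician's judgment guide management. It makes an exception where one of Tables 6-4 to 6-8 calls for discontinuation: there, stopping is compulsory.

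**The concern.** The instruction for a cardiac event points to a lung table. Table 6-7 has no cardiac row and no general-toxicity row. Tables 6-4, 6-5 and 6-6 cover hematological, hepatic and QTcF events, so under Section 6.5.1.2.3 left ventricular dysfunction belongs to Table 6-8. Two current provisions therefore prescribe different actions for the same patient, and a site could cite the protocol for either.

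What is at stake is patient management. Matched by grade number, the literal reading is the more cautious one, so the risk is an unneeded dose reduction or a permanent loss of ribociclib. Matched by label it need not be: Table 6-7 describes grade 1 as asymptomatic, so a reader could make no adjustment for a symptom-free fall in ejection fraction. The rule applies to patients on ribociclib after amendment 4, including those who cross over from placebo.

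**Working it through.** The plan states no figure to reproduce. The check compares the cited table with the one the general rule selects, and then counts where the dose outcome differs.

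**Inputs.** Dose levels from Protocol Table 6-3: 600, 400 and 200 mg, with none listed below 200 mg. Actions come from the rows of Tables 6-7 and 6-8. Assumption: the event is graded 1 to 4 and read against those rows, because the documents give no grading specific to left ventricular dysfunction.

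**Dose after a first occurrence, by starting level (600 / 400 / 200 mg):**

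| Grade | Table 6-7 (cited) | Table 6-8 (general rule) | Levels that differ |
|---|---|---|---|
| 1 | 600 / 400 / 200 | 600 / 400 / 200 | 0 |
| 2 | 400 / 200 / none listed | 600 / 400 / 200 | 3 |
| 3 | stop / stop / stop | 400 / 200 / none listed | 2 |
| 4 | stop / stop / stop | stop / stop / stop | 0 |

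Combinations: 4 grades × 3 levels = 12. Differing: 0 + 3 + 2 + 0 = 5.

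Two cells depend on how the bottom dose level is read. At grade 3 and 200 mg, Table 6-8 asks for a lower level that does not exist, so this is counted as no different from stopping. At grade 2 and 200 mg, Table 6-7 asks for a lower level that does not exist, while Table 6-8 keeps 200 mg; this is counted as different. If that last cell is set aside, 5 − 1 = 4 combinations differ.

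**Recurrence.** Table 6-8 has rules for a repeat event at grades 2 and 3. Table 6-7 has none, so the cited table is also silent on what to do next.

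**Likely origin.** The amendment 4 list of changes records: "Table 6-7 added to include dose adjustment and management recommendations on Interstitial Lung Disease (ILD)/pneumonitis". Section 7.2.2.6.2 already cites Table 7-1b, which the same amendment added. It is plausible that those references were updated and the dose-table number was not. The protocol text as it stood before amendment 4 is not available, so this is an inference. The error does not depend on it, because both conflicting provisions are current text.

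**Effect on the analysis.** SAP Section 3.8.1.1 (primary PFS analysis) does not treat stopping study treatment as a reason for censoring. For OS, Protocol Section 10.5.1 censors only patients not known to have died. Sections 10.4.4, 10.5.1 and 10.7.2 add that both endpoints had already been met and that anything after amendment 4 is descriptive.

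**The case against.** The best case on the other side is that this is an editorial slip with no practical effect. Anyone who follows the reference sees a table headed ILD/pneumonitis and notices the mismatch, and the correct rule is in Section 6.5.1.2.3. Compulsory discontinuation at grade 3 arises only if the wrong reference is accepted first, since left ventricular dysfunction is not itself an event in Table 6-7. The count of 5 in 12 gives equal weight to hypothetical cells and says nothing about how often they occur.

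Much of this stands. The error is a stale cross-reference, not a considered design choice. The count shows where the tables part; it is not a measure of risk. For grade 2, clinical judgment and the benefit-risk footnote leave the physician room.

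It does not remove the point. The sentence in 7.2.2.6.2 is worded as an obligation, and no other text corrects it. Read literally together with Section 6.5.1.2, it leaves no room at grade 3. A reader who does notice the mismatch must still decide alone which of two current provisions governs.

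**Conclusion.** The concern holds as a minor error. The table cited for left ventricular systolic dysfunction is the wrong one, and following it changes the dosing action at grades 2 and 3 and not at grades 1 and 4. Under the grading assumption above, that is 5 of 12 grade-by-dose combinations at first occurrence, or 4 if the grade 2, 200 mg cell is left out. How many patients this touches cannot be estimated: the documents give no event frequency, and Tables 7-1a and 7-1b schedule cardiac imaging after screening only on clinical indication, which suggests few. Sample size, error control and the PFS and OS conclusions are unaffected.

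**What to change.** In Protocol Section 7.2.2.6.2, replace the reference to Table 6-7 with Table 6-8, in line with Section 6.5.1.2.3. If the clinical team wants stricter action for left ventricular dysfunction than Table 6-8 gives, write a specific rule for it with its own grading, rather than borrowing a lung table. The correction costs one table number and needs no new procedures or data collection.

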### 7.2.3 Pharmacokinetics

**Following protocol amendment 4, there will be no more PK blood collection, including patients that cross-over to the LEE011 combination arm.**

Pharmacokinetic blood samples will be obtained from all patients for the analysis of ribociclib (and any relevant metabolites such as LEQ803). Patients will be assigned to the sparse PK collection group or the trough PK collection group.

- Sparse PK collection group: In the sparse PK group, approximately the first 150 patients enrolled will have PK collections as described in [Table 7-6](#).

- Trough PK collection group: In all remaining patients, PK collections will be collected as described in [Table 7-7](#).

Meal conditions (fasting, low fat, high fat) will be recorded within  $\pm$  30 minutes of a dose on the meal record eCRF page for patients assigned to the sparse PK collection group on Cycle 1 Day 15 and Cycle 2 Day 15; the impact of meal conditions on PK in patients may be explored. Refer to [Section 6.1.1.2](#) and [Section 10.6.3](#) for details.

An unscheduled PK blood sample may be collected at any time for measurement of plasma drug concentrations if clinically indicated or at the Investigator's discretion. If a patient discontinues from the study treatment due to toxicities related to study treatment, an unscheduled PK blood sample may be obtained as soon as possible after the last dose and the date and time of last dose recorded. In addition, an unscheduled blood sample may be collected if additional ECG measurements are conducted.

The date and exact time of dosing on PK collection days, as well as the date and actual time of blood sampling must be recorded on the appropriate eCRF pages. In addition, the exact time of dosing on the previous day must be precisely recorded.

If vomiting occurs during the course of treatment, no re-dosing of the patient is allowed, and medication should resume on the next day. The occurrence and frequency of any vomiting must be noted in the adverse events section of the eCRF. In addition, the date and exact time of vomiting should only be recorded if it occurs within 4 hours of dosing on the days of PK sampling. If a vomiting episode occurs within the first 4 hours post-dosing during the day of the last dose prior to trough PK samples the exact time (whenever possible) must be noted on the eCRF. A detailed description of the planned analyses for PK is given in [Section 10.5.4](#).

### **7.2.3.1 Pharmacokinetic blood sample collection and handling**

Blood samples will be obtained from all patients either by direct venipuncture or through an indwelling cannula (e.g., inserted in a forearm vein, or central venous line) for the analysis of plasma concentrations of ribociclib (and any relevant metabolites such as LEQ803), when feasible. At the specified time points described in [Table 7-6](#) and [Table 7-7](#), one single 3mL blood draw will be collected into a tube containing EDTA and gently inverted several times to thoroughly mix the anticoagulant. The blood tube will be centrifuged to separate the plasma. Plasma will immediately be split and transferred into separate pre-labeled tubes for ribociclib. Plasma samples will be stored frozen in an upright position until shipment.

Any sampling problems (e.g., patient took study drug before blood sample, scheduled sampling time is missed, sample is not drawn according to the schedule) should be noted as a comment on the eCRF.

Refer to the [Central Laboratory documents] for detailed instructions for the collection, handling, and shipment of PK samples.

**Table 7-6 Sparse pharmacokinetic blood collection log**

Note: Sparse PK sampling will be performed on approximately the first 150 patients in this study. Blood for Sparse PK profiling will be collected on C1D15 and C2D15 at Pre-dose (0), 2, 4, 6hr, and C2D1 Pre-dose (0hr) for ribociclib/placebo. Only for the sparse PK group, the meal condition (fasting, low fat, high fat) will be collected within ± 30 minutes of the dose on the eCRF on days C1D15 and C2D15.					
Cycle	Day	Scheduled Time Point Relative to Dosing	DRID No. for ribociclib/placebo	PK Sample No. for ribociclib/placebo	Blood Volume (mL)
1	15	Pre-dose a	101/1001 d	101	3
		2h post-dose (± 15 min)	101	102	3
		4h post-dose (± 15 min)	101	103	3
		6h post-dose (± 15 min)	101	104	3
2	1	Pre-dose a	102	105	3
	15	Pre-dose a	103/1003 d	106	3
		2h post-dose (± 15 min)	103	107	3
		4h post-dose (± 15 min)	103	108	3
Unscheduled		Anytime b	NA	1001+	3
		PK samples related to a QTcF ≥ 501 ms c	NA	1051+	3

a. Collect Pre-dose PK sample immediately before drug administration (approximately 24-hrs after the last dose and immediately before the next dose)

b. Unscheduled PK blood samples may be collected at any time for measurement of plasma drug concentrations if clinically indicated or at the Investigator's discretion and will be uniquely, sequentially numbered 1001, 1002, etc., for ribociclib/placebo

c. Unscheduled PK samples related to a QTcF ≥ 501 ms will be uniquely, sequentially numbered 1051, 1052, etc., ribociclib/placebo

d. The first dose reference ID (DRID) No. is for the current dose, while the second DRID No. is for the last dose the subject received prior to the collection of the PK sample

**Table 7-7 Trough pharmacokinetic blood collection log**

Note: Trough PK sampling will be performed in all remaining patients Pre-dose on C1D15, C2D1 and C2D15.					
Cycle	Day	Scheduled Time Point Relative to Dosing	DRID No. for ribociclib/placebo	PK Sample No. for ribociclib/placebo	Blood Volume (mL)
1	15	Pre-dose a	201/2001 d	201	3
2	1	Pre-dose a	202	202	3
	15	Pre-dose a	203/2003 d	203	3
Unscheduled		Anytime b	NA	2001+	3
		PK samples related to a QTcF ≥ 501ms c	NA	2051+	3

a. Collect Pre-dose PK sample immediately before drug administration (approximately 24-hrs after the last dose and immediately before the next dose)

b. Unscheduled PK blood samples may be collected at any time for measurement of plasma drug concentrations if clinically indicated or at the Investigator's discretion and will be uniquely, sequentially numbered 2001, 2002, etc., for ribociclib/placebo

c. Unscheduled PK samples related to a QTcF ≥ 501 ms will be uniquely, sequentially numbered 2051, 2052, etc., ribociclib/placebo

d. The first DRID No is for the current dose, while the second DRID No is for the last dose the subject received prior to the collection of the PK sample

